## 5. SAFETY

Safety analyses will use safety population evaluated by means of AE reports. The analyses of the safety variables will be essentially descriptive, and no statistical testing is planned.

### 5.1. ADVERSE EVENTS

An AE is defined as any untoward medical occurrence in a patient receiving a pharmaceutical product regardless of a causal relationship with this treatment. An AE can therefore be any unfavorable sign and unintended sign (including an abnormal laboratory finding), symptom, or disease temporarily associated with the use of a study treatment, whether or not related to the study treatment.

All AEs (including serious adverse events [SAEs]) will be coded to a preferred term (PT) and associated primary system organ class (SOC) using the MedDRA.

The severity of all AEs will be graded according to the NCI CTCAE Grading Scale, Version 5.0. An AE with a CTCAE grade of 3 or higher is considered a severe AE. The severity of the AE is different from the seriousness of the AE. For AEs not covered by CTCAE, the severity will be characterized as “mild,” “moderate,” “severe”, “life-threatening” (corresponding to Grades 1 to 4) according to the following definitions:

- Mild events are usually transient and do not interfere with the patient’s daily activities.
- Moderate events introduce a low level of inconvenience or concern to the patient and may interfere with daily activities.
- Severe events interrupt the patient’s usual daily activities.
- Life-threatening.

#### 5.1.1. Definitions of Treatment-Emergent Adverse Events (TEAEs), Serious Adverse Events (SAEs), and Treatment-Emergent Treatment-Related Adverse Events (TRAEs)

##### 5.1.1.1. Treatment-Emergent Adverse Event (TEAE)

Treatment-emergent adverse events (TEAE) of study treatment are defined as any event that was not present prior to the initiation of any study treatment (selinexor and/or other drugs) or any event already present that worsens in either intensity or frequency following exposure to study treatment, from the first dose of study treatment to 30 days after the last dose of study treatment inclusive, or the day before the start of a new antineoplastic treatment, whichever occurs first. Additionally, any AEs that occurred 30 days after the last dose of study treatment or after the start of a new antineoplastic treatment will also be considered as TEAE, if assessed by the Investigator as related to any drug of the study treatment.

##### 5.1.1.2. Serious Adverse Event (SAE)

An SAE is any untoward medical occurrence, at any dose, that:

- Results in death

- Is life-threatening (i.e., an event in which the patient was at risk of death at the time of the event; it does not refer to an event that hypothetically might have caused death if it were more severe)
- Requires inpatient hospitalization or prolongation of existing hospitalization
- Results in persistent or significant disability/incapacity
- Results in a congenital anomaly/birth defect

Important medical events that may not result in death, are not life-threatening, or do not require hospitalization may be considered SAEs when, based on appropriate medical judgment, they may jeopardize the patient and may require medical or surgical intervention to prevent one of the outcomes listed in this definition. SAE needs to be clearly documented on the AE form. SAEs that occur at any time between the signing of the ICF up to the first dose of study treatment, must be reported (in addition to SAEs that occur after the first dose of study treatment).

#### **5.1.1.3. Treatment-emergent Treatment-Related Adverse Events (TRAEs)**

A TRAE is any TEAE that is related to any study treatment.

#### **5.1.2. Analysis Methods**

The primary focus of AE reporting will be on TEAEs.

If an AE date/time of onset (occurrence or worsening) is incomplete, an imputation algorithm will be used to determine the AE as treatment-emergent. The algorithm for imputing date/time of onset will be conservative and will classify an AE as treatment-emergent unless there is definitive information to determine it is not treatment emergent. Details on classification of AEs with missing or partial onset dates are provided in Section 2.2.2.

AE summaries will include number (n) and percentage (%) of patients who have experienced an AE. The denominator for computation of percentages is the number of patients in the corresponding treatment arm. Multiple occurrences of the same event in the same patient will be counted only once in the tables.

Unless otherwise specified, sorting order will follow the alphabetic order in SOC, and further by decreasing frequency of PTs within each SOC. When more than one PT has same number of events, the order of presentation will be alphabetical in PTs.

The summary of AEs by causality will generally include the following categories of causality.

- Related to selinexor or pembrolizumab or trifluridine or tipiracil
- Related to selinexor only
- Related to pembrolizumab only
- Related to trifluridine only
- Related to tipiracil only
- Not related to selinexor or pembrolizumab or trifluridine or tipiracil

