**Table 1-1 Study Objectives and Endpoints**

Objectives	Endpoints
Primary 

To evaluate preliminary anti-tumor activity of selinexor with pembrolizumab versus standard of care (SOC)

	

Progression-free survival (PFS), as assessed by the investigator per RECIST1.1 assessed from randomization until disease progression or death from any cause, whichever occurs first

Secondary 

To evaluate preliminary anti-tumor activity of selinexor with pembrolizumab versus SOC

	

Overall survival (OS), defined as time to death due to any cause from the randomization date

ORR, defined as the proportion of patients who achieve complete response (CR) or partial response (PR), per RECIST 1.1 as defined by the Investigator based on radiologic criteria

DCR is defined as the proportion of patients who have best response of PR or better, or at least 12 continuous weeks of SD before disease progression or initiating a new antineoplastic treatment.

PFS at 6 months, OS percent in 6 months, OS percent in 12 months, DOR, and DCR per RECIST 1.1

[figure not shown]

• To evaluate preliminary anti-tumor activity of selinexor only versus SOC

	

• Overall survival (OS), defined as time to death due to any cause from the randomization date

• ORR, defined as the proportion of patients who achieve complete response (CR) or partial response (PR), per RECIST 1.1 as defined by the Investigator based on radiologic criteria

• PFS at 6 months, OS percent in 6 months, OS percent in 12 months, DOR, and DCR per RECIST 1.1

• Progression-free survival (PFS) per RECIST 1.1 assessed by the investigator from the randomization date

• To describe the safety and tolerability of selinexor with and without pembrolizumab

	

• Safety and tolerability of study treatment will be evaluated based on AE reports by the occurrence, nature, and severity of AEs as categorized by the Common Terminology Criteria for Adverse Events (CTCAE) v5.0

Exploratory
 
CCI
 	

CCI

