## **4.2. STATISTICAL METHODS FOR EFFICACY ENDPOINTS**

Binary endpoints of ORR and DCR will be calculated by point estimate with a 95% confidence interval (CI) using the exact method.

The analysis of time-to-event endpoints (PFS, OS, DOR) will be based on Kaplan-Meier method for estimation of summary statistics and will include the median event times and associated 95% CIs, as well as the number and percentage of censored patients. In addition, Cox proportional hazards regression models will be used to estimate a HR for the risk of progression in the selinexor only or selinexor and pembrolizumab arm versus the SOC control arm, and the selinexor and pembrolizumab arm versus selinexor only arm comparisons.

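### Do the drug-specific causality rows in SAP section 5.1.2 need redefining before Arms A and B can be compared?

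*SAP*

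**What the plan says.** Section 5.1.2 states that the summary by causality "will generally include the following categories of causality". Six rows follow:

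- a pooled row, "Related to selinexor or pembrolizumab or trifluridine or tipiracil";
- four single-drug rows: "Related to selinexor only", "Related to pembrolizumab only", the same wording for trifluridine, and "Related to tipiracil only";
- a row for events related to none of the four drugs.

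There is no row for selinexor irrespective of the partner drug, and none for selinexor and pembrolizumab jointly. The word *only* is not defined in 5.1.2, in the TRAE definition (5.1.1.3) or in the rule for missing relationship (2.2.4).

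The categories feed two planned tables by system organ class and preferred term: TEAEs by causality (5.1.3) and treatment-emergent SAEs by causality (5.1.4). Under section 1.1, Arm A receives selinexor alone, Arm B receives selinexor at the same dose plus pembrolizumab, and Arm C receives trifluridine and tipiracil together. The related objective in Table 1-1 is "To describe the safety and tolerability of selinexor with and without pembrolizumab".

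**The concern.** The objective invites a reader to set Arm A beside Arm B. If *only* excludes any other drug, the same row label covers different sets of events in the two columns. Every related event in Arm A is a selinexor-only event, because no other study drug is given. In Arm B an event attributed to both drugs leaves the selinexor row. The effect has one direction: joint attribution can only lower the Arm B row, so selinexor could look less toxic in combination than alone.

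Two smaller points add to the unease. In Arm C the two components share one stated dose, so exclusive rows for each would be of little use. Section 2.2.4 counts an event with missing relationship as related, but does not say which drug row it enters when the patient takes two drugs.

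What would be at stake is a drug-level count that compares like with like in two descriptive tables. Efficacy is not touched.

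**Working it through.** The SAP gives no event rate and no share of joint attributions, so there is no figure of its own to reproduce. The check is set logic on the six rows, with the planned 26 patients per arm from section 1.3.

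**Exclusive reading.** Let S be the events related to selinexor and P those related to pembrolizumab.

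- Arm A: P is empty, so the selinexor row = S.
- Arm B: the selinexor row = S minus (S and P).
- The pooled row is S in Arm A and (S or P) in Arm B. Neither depends on how *only* is read.

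For one preferred term, each Arm B patient whose attribution is joint lowers the selinexor row by 1/26 = 3.8 percentage points. With no joint attributions the row equals S, and the two arms are on the same footing.

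**Can the inclusive Arm B count be recovered from the listed rows?** Take one preferred term with one attribution per patient. Let *a* be selinexor only, *j* joint and *k* pembrolizumab only.

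- Pooled = a + j + k.
- Pooled minus pembrolizumab only = (a + j + k) − k = a + j, the inclusive selinexor count.
- Assumed example: a = 6, j = 2. Pooled = 8 + k, and subtracting k returns 8. The selinexor row itself shows 6.

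At this level the listed rows already determine the count exactly.

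**Several events per patient** (system organ class or any-event level, or repeat occurrences of a term with different attributions). A patient can have one pembrolizumab-only event and another related to selinexor, so subtraction no longer settles the count. Assumed example: pooled 20, pembrolizumab only 10.

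- The 20 − 10 = 10 patients outside the pembrolizumab row must each have a selinexor-related event.
- Of the 10 inside it, 0 to 10 may also have one.
- The inclusive selinexor count is therefore 10 to 20, and the subtraction gives its lower bound.

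For the same share of joint events, the shortfall of the selinexor row is smaller here than for a single term, because one selinexor-only event keeps the patient in the row.

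**Alternative reading.** If *only* means that each drug's relationship is considered by itself, the selinexor row equals S in both arms and the difficulty vanishes.

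**Which reading does the text support?** Elsewhere the SAP uses the phrase for selinexor without pembrolizumab: "To evaluate preliminary anti-tumor activity of selinexor only versus SOC" in Table 1-1, and "the selinexor and pembrolizumab arm versus selinexor only arm comparisons" in section 4.2. Both name a treatment arm, not the attribution of an event. Pointing the other way, separate rows for trifluridine and tipiracil make little sense as exclusive categories for drugs given together. They fit a list with one row per drug. Section 3.4 likewise reports exposure for each of the four drugs separately. Neither set of passages is decisive.

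**The case for a change.** The best case for a change is this. An open list permits an inclusive row but promises none, and two programmers could build different tables from the same words. The SAP chose to tabulate causality by drug, so it ought to do so in a way that serves its own comparison of selinexor with and without pembrolizumab. Subtraction fails above the level of a single term. The remedy needs only wording and table shells, since the listed rows already require causality by drug.

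Part of this stands. The word is undefined, and at system organ class or any-event level the inclusive count cannot be derived from the rows. The rest carries less weight. Table 1-1 defines the safety endpoint by how often adverse events occur, their type and their grade; attribution to a drug is not part of it. The all-TEAE, maximum-grade, SAE and TRAE summaries serve that endpoint directly. An inclusive row would not make the arms fully comparable either: in an open-label study the Arm A investigator has one study drug to blame and the Arm B investigator has two. The gap in section 2.2.4 arises only where the relationship to a particular drug is missing in a two-drug arm. The event still counts as related.

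**Conclusion.** No change to the plan is called for. The observation is right as logic: on the exclusive reading, the selinexor row can be a full count in Arm A and a partial one in Arm B. But the row would be true to its label, the list leaves room for further rows, and the meaning of *only* is the kind of detail that table shells or a footnote settle when the tables are built. An analyst who follows section 5.1.2 as written still produces sound descriptive safety results, and section 5 plans no testing on them.

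The size cannot be fixed from the SAP. It is 3.8 points per jointly attributed patient for a given term, on 26 patients per arm, and zero if no attribution is joint. The count is exactly recoverable for a single term if each patient has one attribution for it; at higher levels it is only bounded. The conclusion rests on the pooled, TRAE and all-TEAE counts carrying the comparison of regimens. They do so under either reading.

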### 5.1.3. Analysis of TEAE

An TEAE overview summary table will be provided, which will include the number of patients with at least one of the adverse events:

- TEAEs
- Grade 3/4 TEAEs
- Serious TEAEs
- TEAEs leading to dose modifications of study treatment
- TEAEs leading to dose reduction of study treatment
- TEAEs leading to dose interruption of study treatment
- TEAEs leading to study treatment discontinuation
- TEAEs leading to death
- TRAE
- Serious TRAEs
- TRAEs leading to dose modifications of study treatment
- TRAEs leading to dose reduction of study treatment
- TRAEs leading to dose interruption of study treatment
- TRAEs leading to study treatment discontinuation
- TRAEs leading to death

TEAEs will be summarized by primary SOC and PT and will include the following categories:

- All TEAEs
- All TEAEs, by causality
- All TEAEs, by maximum grade
- TEAEs leading to dose modifications of study treatment
- TEAEs leading to study treatment discontinuation

### 5.1.4. Analysis of SAE

Treatment-emergent SAEs will be summarized by primary SOC and PT and will include the following categories:

- All treatment-emergent SAEs
- All treatment-emergent SAEs, by causality
- Treatment-emergent SAEs leading to dose modifications of study treatment
- Treatment-emergent SAEs leading to study treatment discontinuation

## **5.2. DEATH**

The following summaries on death events will be provided:

- An overview of all death events and primary cause of death
- TEAEs leading to death by primary SOC and PT
- Listing of all death events

